6.2.2 Clinical Global Impression: Bipolar Version - Severity of Illness (CGI-BP-S)

The CGI-BP-S¹⁴⁾ is a clinician-rated assessment of the patient's current illness state on a 7-point scale, where a higher score is associated with greater illness severity. Following a clinical interview, the CGI-BP-S can be completed in 1 to 2 minutes. A qualified rater at the site will assess the CGI-BP-S at Visits 1 to 8 and at discontinuation. The assessment at Visit 8 or at discontinuation should be performed within 72 hours after the final administration of the study drug and before the initiation of post treatment with antipsychotics, psychotropic drugs or the study drug in the long-term study.

6.2.3 Sheehan Disability Scale (SDS)

The SDS¹⁵⁾ is a composite of 3 self-rated items designed to measure the extent to which 3 major sectors in the patient's life are impaired by depressive symptoms. This anchored visual analog scale uses spatiovisual, numeric, and verbal descriptive anchors simultaneously to assess disability across three domains: work, social life, and family life. At Visits 2 and 8 and at discontinuation, the patient rates the extent to which his or her (1) work, (2) social life or leisure activities, and (3) home life or family responsibilities are impaired by his or her symptoms on a 10-point visual analog scale. The assessment at Visit 8 or at discontinuation should be performed within 72 hours after the final administration of the study drug and before the initiation of post treatment with antipsychotics, psychotropic drugs or the study drug in the long-term

study. There are verbal descriptors for the points on the scale as well as numerical scores that provide more precise levels of the verbal descriptors.

6.2.4 Young Mania Rating Scale (YMRS)

The YMRS ¹⁶⁾ is an 11-item instrument used to assess the severity of mania in patients with a diagnosis of bipolar disorder. The 11 items are: elevated mood, increased motor activity energy, sexual interest, sleep, irritability, speech (rate and amount), language-thought disorder, content, disruptive-aggressive behavior, appearance and insight. The YMRS is a clinician-rated assessment. The YMRS uses operationally-defined anchor points. Ratings are based on patient self-reporting, combined with clinician observation (accorded greater score). The Concordant YMRS Structured Interview Guide will be used for the YMRS assessment.

A qualified rater at the site will assess the YMRS at Visits 1 to 8 and at discontinuation. The assessment at Visit 8 or at discontinuation should be performed within 72 hours after the final administration of the study drug and before the initiation of post treatment with antipsychotics, psychotropic drugs or the study drug in the long-term study. The rater should receive specific training for the YMRS assessment provided by the sponsor and will be required to be certified by the sponsor before his or her initial assessment of the YMRS.

6.2.5 Hamilton Rating Scale for Anxiety (HAM-A)

The HAM-A ¹⁷⁾ is a rating scale developed to quantify the severity of anxiety symptomatology. It consists of 14 items, each defined by a series of symptoms. Each item is rated on a 5-point scale, ranging from 0 (not present) to 4 (severe/disabling). The Structured Interview Guide for the HAM-A (SIGH-A) will be used for the HAM-A assessment. A rater at the site will assess the HAM-A at Visits 2 and 8 and at discontinuation. The assessment at Visit 8 or at discontinuation should be performed within 72 hours after the final administration of the study drug and before the initiation of post treatment with antipsychotics, psychotropic drugs or the study drug in the long-term study.

6.3 Pharmacokinetic measurements

Serum concentrations of SM-13496 and its metabolites will be determined in only patients who provide informed consent for blood sampling for pharmacokinetics. To maintain the blind, the laboratory ([REDACTED]) will report the serum concentration data to the sponsor after unblinding the treatment code.

1) Measurement

Serum concentration of SM-13496 and its major metabolites (hydroxylated products [ID-14283 and ID-14326], cleaved product [ID-11614])

2) Blood sampling

At Visits 5, 6 and 8, and at discontinuation (if after Week 3), 10 mL of blood will be collected from a vein at 13 to 15 hours after the administration of the study drug.

3) Recording

The following information will be recorded in eCRFs: date and time of blood sampling, time of taking the study drug on the day before the sampling.

6.4 Safety measurements

6.4.1 Adverse events

6.4.1.1 Definitions

The definitions of adverse events (AEs) and serious adverse events (SAEs) are shown below. It is of the utmost importance that all staff members involved in the study are familiar with the content of this section. The principal investigator will be responsible for ensuring that all site staff have read and understand this content.

Adverse events (AEs)

An adverse event (AE) is any untoward medical occurrence in a patient treated with a medicinal (investigational) product and which does not necessarily have a causal relationship with this treatment. An AE can, therefore, be any unfavorable and unintended sign (eg, an abnormal laboratory finding), symptom, or disease occurring after the administration of a medicinal (investigational) product, whether or not considered related to the medicinal (investigational) product. AEs may include the onset of new illness and the exacerbation of pre-existing conditions.

Lack of efficacy may be an expected potential outcome and should not be reported as an adverse event unless the event is unusual in some way.

The investigator should attempt to establish a diagnosis of the event based on signs, symptoms, and/or other clinical information. In such cases, the diagnosis should be documented as the AE and not the individual signs/symptoms.

Serious adverse events (SAEs)

A serious adverse event (SAE) is an AE that meets one or more of the following criteria:

- Results in death.
- Is life-threatening (ie, a patient is at immediate risk of death at the time of the event, not an event where occurrence in a more severe form might have caused death).
- Requires hospitalization or prolongation of existing hospitalization.
- Results in persistent or significant disability or incapacity.
- Is a congenital anomaly or birth defect.
- Is an important medical event that may jeopardize the patient or may require a medical or surgical intervention to prevent one of the outcomes listed above. Examples of such medical events include allergic bronchospasm requiring intensive treatment in an emergency room or at home, blood dyscrasias or convulsions that do not result in inpatient hospitalization.

The term "severe" is often used to describe the severity of a specific event (as in mild, moderate, or severe myocardial infarction) (see Section 6.4.1.3, Page 52); the event itself, however, may be of relatively minor medical significance (such as severe headache). This is not the same as "serious," which is based on subject/event outcome or action criteria usually associated with events that pose a threat to a subject's life or functioning as defined by the criteria above.

During the study, if a patient has a hospitalization or procedure (eg, elective surgery) that was scheduled before the study entry, ie, before informed consent for an event/condition that occurred before the study, the hospitalization is considered a therapeutic intervention and not the result of a SAE. However, if the event/condition worsens during the study, it should be reported as an AE (or SAE, if the event/condition results in a serious outcome such as prolongation of hospitalization).

Life-threatening means that the patient was, in the view of the investigator, at immediate risk of death from the event as it occurred. This definition does not include an event that had it occurred in a more severe form might have caused death.

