4.3 Discontinuation of patients from the study

4.3.1 Discontinuation criteria

Patients may be discontinued from the study treatment and assessments at any time for any of the following reasons:

- Adverse event
- Lack of efficacy
- Pregnancy
- Withdrawal by patient
- Noncompliance
- Protocol violation
- Lost to follow-up
- Other

The investigator should terminate the study treatment if a female patient becomes pregnant (see Section 7.2, Page 59) or if any adverse events or lack of efficacy results in psychotic hospitalization.

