16.1.3. SERIOUS ADVERSE EVENTS

Serious adverse events (SAEs) are those events recorded as "Serious" on the Adverse Events page of the eCRF. A summary of serious TEAEs by SOC and PT will be prepared. A listing will provide details of SAEs and indicate any drug relationship.

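### The lack-of-efficacy rule has no exception for serious events, so whether an admission for worsening depression is counted as an SAE depends on the label the site gives it

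*Protocol*

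**What the plan says.** Five statements bear on this point.

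- **The rule.** Protocol Section 6.4.1.1: "Lack of efficacy may be an expected potential outcome and should not be reported as an adverse event". The sentence carries one qualification, so its full instruction is that lack of efficacy "should not be reported as an adverse event unless the event is unusual in some way". *Unusual* is not defined.
- **What an AE can be.** The same section: "AEs may include the onset of new illness and the exacerbation of pre-existing conditions".
- **What an SAE is.** The same section: "A serious adverse event (SAE) is an AE that meets one or more of the following criteria". One criterion is "Requires hospitalization or prolongation of existing hospitalization".
- **Stopping treatment.** Protocol Section 4.3.1 has the investigator end study treatment "if any adverse events or lack of efficacy results in psychotic hospitalization". I take the adjective to mean psychiatric. Adverse events and lack of efficacy appear there as two separate causes, and no AE or SAE reporting instruction is attached to the second.
- **The table.** SAP Section 16.1.3: "A summary of serious TEAEs by SOC and PT will be prepared". The events that feed it are those marked serious on the AE page of the case report form.

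Section 6.4.1.1 also has a paragraph on hospitalisations scheduled before study entry. It says that "if the event/condition worsens during the study, it should be reported as an AE", or as an SAE where the outcome is serious.

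**The concern.** In a placebo-controlled trial in bipolar depression, worsening of the illness to the point of admission is among the most relevant serious outcomes. Whether it counts as a serious event should not turn on which of two labels an investigator picks.

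Two consequences follow if it does. First, the SAE comparison can be incomplete, and unevenly so. If the drug works, lack of efficacy should be more common on placebo, so more placebo admissions could be left out. If instead the drug worsened depression in some patients, those events could be labelled as non-response and leave the SAE comparison. Second, Protocol Section 7 lists SAEs, pregnancy and overdose as immediately reportable. An admission that is not classed as an SAE does not trigger the 24-hour report in Section 7.1. SAP Section 4.1 confirms that there is no data monitoring committee that might pick it up during the trial.

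**Working it through.** This is a check of the text; the plan states no figure to reproduce. Take an outpatient whose depression worsens in the treatment phase and who is admitted, and follow the rules under each label.

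**Route A: the investigator calls it lack of efficacy and does not consider it unusual.**
1. Section 6.4.1.1: it is not reported as an AE.
2. SAEs are a subset of AEs, so it cannot be an SAE, although the patient was hospitalised.
3. Section 7.1: no 24-hour report is due.
4. SAP Section 16.1.3: nothing on the AE page, so it is not in the SAE summary or listing.
5. SAP Section 16.1.2: TEAEs leading to discontinuation come from the action-taken field of an AE record. There is no AE record, so it is not there either.
6. Protocol Section 4.3.2 and SAP Section 9: it appears as a discontinuation for lack of efficacy, alongside patients who simply did not respond.

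**Route B: the investigator calls it a worsening of an existing illness, or considers the admission unusual.**
1. Section 6.4.1.1: it is an AE.
2. Hospitalisation is a seriousness criterion, so it is an SAE.
3. The 24-hour report is due and the event enters the SAE summary.

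The same facts end in two different places, and nothing in Section 6.4.1.1 says which route prevails when both descriptions fit. The paragraph on pre-scheduled hospitalisations points towards Route B, but it is written for a different situation. Section 4.3.1 foresees hospitalisation through lack of efficacy without saying how it is to be reported.

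**Size.** Let *a* be the proportion of patients admitted for worsening depression, *b* the proportion with some other SAE (no overlap), and *f* the share of those admissions labelled lack of efficacy. The share of patients with serious events who are missed is *f* × *a* / (*a* + *b*). The documents give none of the three. Purely as an assumption, take *a* from 0.5% to 2% (0.8 to 3.3 of the 167 patients planned per arm) and *b* = 1%:

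| *f* | *a* = 0.5% | *a* = 2% |
|---|---|---|
| 0 | 0% | 0% |
| 1 | 0.5/1.5 = 33% | 2/3 = 67% |

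The result runs from 0% to 67%, according to what is assumed for *f* and *a*. It shows that the label decides the answer; it is not an estimate of the loss.

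**The case against.** The strongest reply is that the section already provides for reporting. Just before the lack-of-efficacy sentence it allows worsening of an existing illness to be an AE, and it then makes hospitalisation a seriousness criterion. Failing to improve is not the same as deteriorating, and an outpatient admitted within six weeks can readily be called unusual. Section 4.3.1 governs stopping treatment and exempts nothing from SAE reporting.

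This stands to the extent that it defeats a stronger reading that a reader might infer: that the protocol flatly excludes such admissions, so that a site following it must leave them off the AE page. The exception for unusual events and the wording on worsening both contradict that. What the reply does not do is close Route A. *Unusual* is undefined, seriousness is not mentioned in the exception, and Section 4.3.1 accepts that lack of efficacy can itself lead to hospitalisation.

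A second reply is that the event leaves traces elsewhere. The reason for discontinuation is summarised, MADRS and CGI-BP-S are rated at discontinuation, MADRS change is plotted by visit of discontinuation (SAP Section 15.1.3.1), and suicidality is tabulated by arm from the C-SSRS (SAP Section 16.7.4). That is correct, and the event is not lost altogether. But none of these outputs identifies an admission. Treatment-emergent mania has its own safety summary (SAP Section 16.7.5); serious depressive worsening has none.

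**Conclusion.** The concern holds as an ambiguity with a safety consequence. An admission for worsening depression may be recorded only as a discontinuation for lack of efficacy, and so miss the SAE tables and the 24-hour report. It may equally be recorded as an SAE. The documents support both, so counting depends on the site's label and could differ by arm.

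The under-count cannot be estimated. No admission rate, and no share handled under either label, is given, and if sites use the worsening wording the loss is zero. A reader might infer from the table above that a third or more of serious events would go missing. That holds only if every such admission is labelled lack of efficacy, which nothing in the documents establishes. The direction of any bias is also open: dropping placebo admissions would hide a benefit of the drug, while relabelling drug-related worsening would hide a harm.

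This is a cheap improvement to safety reporting and does not affect the primary efficacy analysis.

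**What to change.** **Protocol.** Reconcile Section 4.3.1 with the two parts of Section 6.4.1.1 (the lack-of-efficacy rule and the paragraph on pre-scheduled hospitalisations) by adding, directly after the lack-of-efficacy sentence:

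> Any worsening of depression or other bipolar symptoms that meets a seriousness criterion, including hospitalisation, is recorded as an AE and reported as an SAE, even where the investigator attributes it to lack of efficacy.

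This changes only what is recorded and reported; the rule on stopping treatment is untouched.

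**SAP.** In Section 16.1.3, summarise patients with a psychiatric hospitalisation by arm, drawn from those SAE records. The SAE report in Protocol Section 7.1 already carries the criterion that made the event serious. A count independent of the SAE records is not recommended: outside that criterion, the protocol describes hospitalisation data only as screening history (Section 6.1), so it would need a new case report form field.

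**Timing.** The SAP gives 20 February 2017 as last patient last visit and is itself dated 30 March 2017. For data already collected, the practical equivalent is a query, before unblinding, on each discontinuation for lack of efficacy, asking whether the patient was admitted.

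**Cost.** One sentence and a site memo, a few more SAE forms, one short summary, and slightly higher reported SAE rates. The query adds a small amount of data management work.

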6.4.1.2 Objective findings

Clinically significant abnormal objective findings (eg, clinical laboratory value, ECG value, and physical examination observation) will also be recorded as AEs.

When a clear diagnosis is available that explains the objective findings, this diagnosis will be recorded as the AE, and not the abnormal objective finding (eg, viral hepatitis will be recorded as the AE, not transaminase elevation). If a definite diagnosis is not available, then record the sign (eg, clinically significant elevation of transaminase levels) or symptom (eg, abdominal pain) as the AE.

Clinical laboratory test results will be reviewed by the investigator. The investigator should determine the clinical significance of all out of range values. Clinical laboratory test with possibly drug-related or clinically relevant abnormal values of uncertain causality may be repeated. Any abnormal values that persist should be followed at the investigator's discretion.

All on-site ECG tracings and ECG reports by the ECG parameter measurement center will be reviewed by the investigator. The investigator should determine the clinical significance of all abnormal ECGs. ECG with possibly drug-related or clinically relevant abnormal findings of uncertain causality may be repeated. Any abnormal ECGs that persist should be followed at the investigator's discretion.

6.4.1.3 Collection and recording of adverse events

AEs will be collected for each patient from the time the informed consent is obtained until the last study visit. Patients should be queried in a non-leading manner, without specific prompting (eg, "Has there been any change in your health status since your last visit?"). AEs and SAEs will be monitored throughout the study at all visits.

All AEs should be collected and recorded in the patient's study records/source documents, in accordance with the investigator's normal clinical practice, and in the eCRFs.

Each AE will be evaluated for duration, severity, seriousness, action taken with the study treatment, outcome, and causal relationship to the study treatment. Definitions for severity, action taken with the study treatment, outcome, and causal relationship to the study treatment are presented below. When the severity of an AE which has an onset before the treatment phase worsens after the initiation of the treatment phase, the more severe AE should be captured as a new AE.

Severity of AE

- **Mild** – Ordinarily transient symptoms that do not influence performance of patient’s daily activities. Other treatment is not ordinarily indicated.
- **Moderate** – Marked symptoms sufficient to make the patient uncomfortable. Moderate influence on performance of patient’s daily activities. Other treatment may be necessary.
- **Severe** – Symptoms cause considerable discomfort. Substantial influence on patient’s daily activities. May be unable to continue the study, and other treatment may be necessary.

When the severity of an AE changes, the maximum severity for the event should be noted.

The action taken with the study treatment:

- **Drug Withdrawn** – Study drug stopped permanently.
- **Dose Reduced**
- **Dose Increased**
- **Dose Not Changed**
- **Not Applicable**

The outcome of the AE:

- **Recovered/Resolved**
- **Recovering/Resolving**
- **Not Recovered/Not Resolved**
- **Recovered/Resolved with Sequelae**
- **Fatal**
- **Unknown**

The causal relationship of the AE to the study treatment:

- **Not related**
 - **Not related** – Improbable temporal relationship and is plausibly related to other drugs or underlying disease.
 - **Unlikely** – occurred within a reasonable time frame after administration/discontinuation of the study drug, but there is a likely association of an intercurrent/underlying medical condition or other drugs.

- Related

- **Possible** – occurred in a reasonable time after study drug administration, but could be related to concurrent drugs or underlying disease.
- **Probable** – occurred in a reasonable time after study drug administration, is unlikely to be attributable to concurrent drugs or underlying disease, and there is a plausible mechanism to implicate the study drug.
- **Definite** – occurred in a reasonable time after study drug administration and cannot be explained by concurrent drugs or underlying disease. The AE should respond to dechallenge/rechallenge, however, this is not mandatory before assigning a definite causality.

The medical monitor is the initial contact person for protocol related questions or discussion of AEs.

6.4.1.4 Follow-up of AEs

Appropriate measures should be taken as necessary to treat AEs, and the response of the patient should be monitored as medically appropriate, as well as recorded. Clinical laboratory and diagnostic measures should be obtained as needed.

All AEs will be followed until resolution, stabilization of the condition, the event being otherwise explained, or the patient being lost to follow-up.

6.4.2 Laboratory tests

Blood and urine samples for the laboratory test will be collected at Visits 1, 2, 3, 6, 8, and at discontinuation, and will be submitted to the central laboratory for analysis. At Visit 8 or at discontinuation, the samples should be collected within 72 hours after the final administration of the study drug and before the post treatment with antipsychotics. At Visits 2 and 8 or at discontinuation, blood samples will be collected in a fasting condition. Collection and handling of blood samples will be performed in accordance with the routine procedures and the separately provided instructions.

The central laboratory will analyze the samples for the tests listed in Table 6.

Table 6 Contents of the laboratory variables

Hematology	Red blood cell count, white blood cell count, hemoglobin, hematocrit, platelet count, white blood cell classification (ie, neutrophils, eosinophils, basophils, monocytes, and lymphocytes)
Blood chemistry test	AST, ALT, ALP, γ -GTP, total protein, total bilirubin, BUN, creatinine, total cholesterol, LDL cholesterol, HDL cholesterol, triglycerides, LDH, CK, blood glucose, uric acid, HbA1c, glycoalbumin, prolactin, albumin, insulin, electrolytes (Na, K, Cl),
Endocrine	Thyroid stimulating hormone (TSH), free thyroxine (FT4), total and free testosterone
Hepatitis	HBs antigen, HCV antibody (Low positive HCV antibody will be confirmed by INNO-LIA method.)
Urinalysis (qualitative tests)	Protein, glucose, urobilinogen, occult blood

Prolactin, HbA1c (NGSP), glycoalbumin, blood glucose, total cholesterol, LDL cholesterol, HDL cholesterol, and triglycerides will be measured only at Visits 1, 2 and 8 and at discontinuation. Blood glucose will be measured in fasting condition at Visits 2 and 8 and at discontinuation. TSH, FT4, and total and free testosterone will be measured only at Visits 1 and 8 and at discontinuation. Hepatitis tests will be performed only at screening.

The prolactin concentration data will not be disclosed until all the other data is locked to ensure the study blindness, as antipsychotics often increase prolactin concentrations, and will be reported to the investigators and the sponsor.

Pregnancy test (urine chorionic gonadotropin) will be performed in female patients of childbearing potential before menopause at the study site at Visits 1 and 8 and at discontinuation. If urine pregnancy test is positive, serum pregnancy test will be performed.

Total and free testosterone will be measured only in male patients.

